3.1.7. Microbiologically Evaluable (ME) Populations

The ME-Day 5, ME-EOI, ME-EOT, ME-TOC and ME-FU populations will consist of all subjects in the micro-ITT and the CE-Day5, CE-EOI, CE-EOT, CE-TOC, CE-FU populations, respectively who also meet the following:

- Had a suitable urine specimen (as defined in [Section 3.1.4](#)) collected at the Day 5 (ME-Day 5), EOI (CE-EOI), EOT (ME-EOT), TOC (ME-TOC) and FU (ME-FU) Visits. Subjects who are microbiological failures prior to the TOC or FU Visit, and are otherwise evaluable, will be included in the ME-TOC and ME-FU populations regardless of when the TOC and FU visits occurred.
- The urine culture at the Day 5 (ME-Day 5), EOI (ME-EOI), EOT (ME-EOT), TOC (ME-TOC) and FU (ME-FU) Visits is interpretable with respect to determining microbiological outcome. An interpretable urine culture is one that has a clearly identified pathogen or one where the baseline pathogen(s) can be excluded. A urine culture will be considered uninterpretable if more than 2 bacterial isolates are identified unless the specimen is obtained via suprapubic aspiration, nephrostomy tube newly placed or cystoscopy, 1 of the isolates comprises $\geq 80\%$ of the total growth (predominant), 1 or more isolates are also isolated simultaneously from a blood culture, or there is $< 10^4$ CFU/mL (including no growth) of the baseline pathogen(s).

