5.7.1. Primary Efficacy Analysis

The primary outcome measure is a responder outcome derived from both clinical response and microbiological response at the EOI and the TOC Visit in the micro-ITT population.

Clinical Response:

Clinical response is based on the Investigator Responses on the CRF and is not derived programatically. Clinical response is classified by the Investigator as cure, failure or indeterminate based on the following definitions:

- **Clinical Cure:** Clinical cure is defined as complete resolution or significant improvement of signs and symptoms of the infection such that no rescue/non-study antibacterial therapy is required to treat the cUTI that presented at study entry

- **Clinical Failure:** Subjects are classified as a clinical failure based on:
 - Death related to cUTI at any time point
 - Persistence of clinical symptoms of cUTI or new symptoms have developed
 - Initiation of rescue/non-study antibacterial drug therapy for cUTI
- **Indeterminate/Missing:** If the subject's outcome is neither clinical cure nor clinical failure, then the outcome should be listed as indeterminate/missing, including death where the cUTI is clearly noncontributory. If the Investigator did not complete an assessment or if the subject did not complete the study visit, the outcome is considered missing

Subjects who are assessed as a clinical failure at the EOT visit or beyond will have the failure carried forward to all subsequent visits.

Data for all subjects will be reviewed to ensure the Investigators are following the protocol defined criteria for clinical response and queries will be issued as needed to clarify any response that does not meet the protocol definition.

Microbiologic Response:

Per-subject microbiological response is defined as follows:

- **Microbiological success:**
 - Reduction of the baseline pathogen(s) to $<10^4$ CFU/mL
- **Microbiological failure:**
 - Blood cultures are positive for the baseline pathogen(s), or
 - Urine culture grows $\geq 10^4$ CFU/mL of the baseline pathogen(s)
- **Microbiological Indeterminate/Missing:** No interpretable urine culture data are available

The primary efficacy outcome is defined in [Table 5](#).

Table 5 Primary Efficacy Outcome

Primary Efficacy Outcome		
Clinical Response	Microbiological Response	Responder Outcome
Cure	Success	Responder
Cure	Failure	Non-responder
Cure	Indeterminate / Missing	Indeterminate
Failure	Success	Non-responder
Failure	Failure	Non-responder

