Where n_{1i} is the number of subjects in the eravacycline treatment group (Group 1) in the i -th stratum, and n_{2i} is the number of subjects in the ertapenem treatment group (Group 2) in the i -th stratum.

The second sensitivity analysis will analyze those subjects who are considered indeterminates in the primary analysis as responders. Additional sensitivity analyses will be stratified analyses for the following combinations: primary site of infection and geographic region, primary site of infection and receipt of a single dose of effective non-study antibiotics, and geographic region and receipt of a single dose of effective non-study antibiotics. Two-sided 95% CIs will be computed for the difference in responder rate at the EOI and TOC visits between the eravacycline and ertapenem treatment groups within each stratum using the method of Miettinen and Nurminen.

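### For mixed-growth urine cultures that meet no other exemption, SAP 3.1.7 keeps a success in the ME population and removes a failure

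*SAP*

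**What the plan says.** SAP 3.1.7 requires an interpretable urine culture at the visit for each ME population. Its general test is: "An interpretable urine culture is one that has a clearly identified pathogen or one where the baseline pathogen(s) can be excluded". A specific rule follows: "A urine culture will be considered uninterpretable if more than 2 bacterial isolates are identified unless the specimen is obtained via suprapubic aspiration". The same exemption covers newly placed nephrostomy tubes and cystoscopy. The list goes on to one isolate at 80% or more "of the total growth (predominant), 1 or more isolates are also isolated simultaneously from a blood culture", and ends with a count below 10^4 CFU/mL of the baseline pathogen, absence of growth included. Otherwise evaluable subjects who were microbiological failures before TOC or FU are kept in ME-TOC and ME-FU.

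SAP 5.7.1 defines success as "Reduction of the baseline pathogen(s) to" below 10^4 CFU/mL. Failure is a positive blood culture for the baseline pathogen, or "Urine culture grows" that pathogen at 10^4 CFU/mL or more, with no limit on the number of other isolates. Protocol 11.1.6 uses the same thresholds. The SAP's indeterminate category reads: "No interpretable urine culture data are available".

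Under SAP 4.6, microbiological indeterminates are excluded from ME but stay in the micro-ITT and micro-MITT denominators as failures. SAP 3.2.2 has ME membership derived by program.

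**The concern.** The first three exemptions concern how the specimen was taken or what else was found. The fourth is the endpoint itself. A subject whose culture falls in the affected class is therefore kept or dropped according to whether the result is a success or a failure. The rule can remove only failures, so it raises ME success rates. Even when it acts equally in both arms it shrinks a true deficit, because the worse arm has more failures to lose. In a non-inferiority comparison that is the unsafe direction.

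In this SAP the ME comparisons are descriptive. Under Protocol 15.2.1, however, microbiological success at TOC in ME is co-primary for the EMA, alongside micro-MITT.

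There is a second, conditional consequence. SAP 5.7.1 does not say whether the 3.1.7 rule defines interpretability there. If it does, a clinical cure with a failure-level culture of this class is indeterminate in SAP Table 5. SAP 5.7.1.1 then says: "The second sensitivity analysis will analyze those subjects who are considered indeterminates in the primary analysis as responders". That subject would count as a responder although the baseline pathogen grew at failure level.

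**Working it through.** **1. The rule applied to two specimens.** Take two clean-catch midstream cultures, each with three isolates, none at 80% of growth, and no simultaneous blood isolate.

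| Baseline pathogen | SAP 5.7.1 thresholds | SAP 3.1.7 | ME at that visit |
|---|---|---|---|
| 10^3 CFU/mL | success | interpretable (fourth exemption) | kept |
| 10^5 CFU/mL | failure | uninterpretable | dropped, unless already a failure before TOC or FU |

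The more-than-2-isolates rule for baseline cultures in SAP 3.1.4 has the first three exemptions but not the fourth. The result-based exemption appears only after baseline.

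**2. Inputs.** SAP 4.1 and Table 3 give 720 subjects in ME, 82% success in both arms, a 10-point margin and one-sided alpha 0.005. With 1:1 allocation that is 360 per arm, so 360 × 0.18 = 64.8 expected failures per arm. The share f of failures that fall in the affected class is not in the documents. I assume 5% to 20%.

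**3. Nearest stated figures.** Farrington-Manning power reproduces the micro-MITT row (79.8% at 390 per arm). For ME it gives 81.1% at 360 per arm against the stated 84.7%; 390 per arm gives 84.7%. The ME row thus appears to have been computed at the micro-MITT size. This is a separate matter and does not affect what follows.

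**4. Effect on a rate.** Dropping a share f of failures turns a success rate p into p / (1 − (1 − p)f).

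For p = 0.82:
- f = 5% (64.8 × 0.05 = 3.2 failures per arm): 0.82 / 0.991 = 82.7%
- f = 10% (6.5 per arm): 0.82 / 0.982 = 83.5%
- f = 20% (13.0 per arm): 0.82 / 0.964 = 85.1%

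**5. Effect on a true deficit at the margin.** Take ertapenem at 82%, eravacycline at 72%, and f equal in both arms. Type I error is the Farrington-Manning rejection probability at nominal one-sided 0.005, for the ME test alone.

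| f | Eravacycline | Ertapenem | Difference, points | Type I error, ME alone |
|---|---|---|---|---|
| 0 | 72.0% | 82.0% | −10.0 | 0.0050 |
| 5% | 0.72 / 0.986 = 73.0% | 82.7% | −9.7 | 0.0065 |
| 10% | 0.72 / 0.972 = 74.1% | 83.5% | −9.4 | 0.0084 |
| 20% | 0.72 / 0.944 = 76.3% | 85.1% | −8.8 | 0.0148 |

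**6. Where the effect stops.** In micro-ITT, indeterminate and failure are both non-response in the primary analysis, so the responder rate does not change. In micro-MITT the subject stays in the denominator as a failure, so that success rate cannot rise.

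**The case against.** The strongest defence is microbiological. Contamination can add organisms to a specimen but cannot hide a baseline count. A count below 10^4 in mixed growth therefore remains informative, while a count at or above 10^4 may be ambiguous. That justifies keeping the successes. It does not justify discarding a culture in which the known baseline pathogen has been identified and quantified at failure level, and which the general test in 3.1.7 would accept. Blinded committee review does not cure this: membership is programmed from the written rule, and blinding to arm does not prevent selection on outcome.

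Other limits on the point stand in full:

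- A reader might infer that every failure-level culture with more than 2 isolates leaves ME. It does not. Failures under any of the first three exemptions stay, as do otherwise evaluable subjects who failed before TOC or FU.
- A reader might infer that inflated ME rates could deliver an EMA claim on their own. Protocol 15.2.1 requires both populations to pass, and micro-MITT gets no help from this rule. SAP 1.1.1 also leaves the EMA analysis to a separate SAP that is not among the documents.
- A reader might infer a flat contradiction between 3.1.7 and the failure definitions. SAP 5.7.1 and Protocol 11.1.6 each have a category for no interpretable culture data, so the sections can be reconciled if 3.1.7 governs interpretability. The sensitivity-analysis problem arises only on that same reading. The two complaints cannot both hold; what is missing is the link between the sections.
- A reader might infer a spurious advantage for eravacycline. With f = 20% on eravacycline and 5% on ertapenem, equal true rates would show 85.1% − 82.7%, or +2.3 points before rounding. That needs a fourfold imbalance between blinded arms, for which the documents offer no reason.

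**Conclusion.** The point holds for one class of culture: more than 2 isolates, not collected by suprapubic aspiration, new nephrostomy or cystoscopy, no isolate at 80% or more of growth, and no simultaneous blood isolate. Within that class, following the SAP as written selects the ME population on its own outcome.

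The direction is certain: ME success rates rise and, at equal shares, a true deficit shrinks. The size is not. It depends on f, and the planning values of 360 per arm and 82% already describe ME as currently defined, so the worked figures are illustrative. At small shares the distortion is modest.

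The documents do not support a claim that the FDA primary conclusion is at risk. The EMA effect is confined to the ME half of the test and depends on the unseen EMA SAP. The effect on the second sensitivity analysis depends on how 5.7.1 is read. This is worth correcting because the remedy is simple, not because it threatens the main result.

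**What to change.** State in SAP 3.1.7 and 5.7.1 that a post-baseline urine culture in which a baseline pathogen is identified and quantified at 10^4 CFU/mL or more is interpretable and is a microbiological failure, whatever the number of other isolates. Reserve the uninterpretable category for cultures in which the baseline pathogen count cannot be determined. Apply this to every ME visit population and to the micro-ITT responder derivation, and carry it into the EMA SAP and the Microbiological Outcomes Review Plan. Report ME under the current rule as a sensitivity analysis.

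The change needs a short SAP amendment before database lock and no new data. Its drawback is that some contaminated specimens will count as failures. That slightly lowers ME success rates and, if it happens at random in both arms, may slightly dilute a true difference; the sensitivity analysis shows how much turns on this. The alternative of excluding all such cultures whatever their result would also remove the selection, provided their frequency is unrelated to outcome. It costs power, however: from 81.1% at 360 per arm to 78.6% if 5% of cultures are lost and 75.9% if 10% are.

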3.2. Evaluability Review

3.2.1. Membership and Responsibilities

The MRC will be responsible for reviewing microbiological data, including pathogen determination, as outlined in the Microbiological Outcomes Review Plan. The Evaluability Review Committee (ERC) will review clinical and microbiological data to assess inclusion in or exclusion from the CE populations as outlined in the Clinical Evaluability Review Plan. MRC and ERC members will be blinded to treatment assignment and will review the data concurrent with the conduct of the study. Final pathogen determinations and inclusion in analysis populations will be determined prior to database lock except for those criteria which require unblinded data (for example, determination of whether or not the subject received the study drug to which s/he was randomized).

3.2.2. Process for Determining Inclusion in Analysis Populations

Inclusion into the ITT and Safety populations will be determined programmatically from the eCRF data. Inclusion into the CE populations will be determined programmatically from the eCRF data and the manual review conducted by the ERC.

Inclusion into the micro-ITT population will be determined programmatically by incorporating the outcome of the review of the isolates by the MRC. The MRC will determine whether each

isolate (baseline and post-baseline) is considered a pathogen based on a review of information regarding baseline samples such as method of collection of the specimen, CFU/mL, local and central genus and species identification. Inclusion into the ME and micro-MITT populations will be determined programmatically.

3.3. Protocol Deviations

Deviations will be reviewed by the Sponsor and categorized into general categories such as: informed consent, inclusion/exclusion criteria, randomization procedure, subject visit completion or timing, study procedure or assessment, study medication, excluded concomitant medication, and (serious) AE reporting. The number of subjects with at least 1 protocol deviation, the number of subjects with a minor protocol deviation, the number of subjects with a major deviation, and the number of subjects with at least 1 major deviation in each category will be presented by treatment group for the ITT population. A major deviation is defined as one that potentially affects the efficacy and/or safety analyses and will be determined by a review by the Sponsor in accordance with the Protocol Deviations Review Plan.

All protocol deviations will be presented in a data listing.

4. GENERAL STATISTICAL METHODS

4.1. Sample Size Justification

This study is designed to demonstrate NI of eravacycline to ertapenem in the co-primary efficacy measures of responder outcome at the EOI and TOC visits in the micro-ITT population. An NI margin of 10% will be used which is based on historical data regarding the treatment effect of antibiotics. A 10% NI margin for the efficacy measure of responder outcome is robust and can sufficiently confirm a clinically meaningful treatment effect of eravacycline in the treatment of cUTI.

The sample size calculation is based on ensuring sufficient power for the co-primary efficacy outcomes for the FDA as well as the co-primary efficacy outcomes for the EMA (which are secondary efficacy outcomes for the FDA). Using a 10% NI margin, one-sided alpha of 0.025, 80% power, response rates at TOC of 71% in the eravacycline group and 72% in the ertapenem group, and the sample size methodology of Farrington and Manning, a total of 395 subjects per arm in the micro-ITT population is required. This sample size provides >90% power for the response rates at EOI assuming the response rates are 93% and 94% in the eravacycline and ertapenem groups, respectively. A sample size of approximately 1200 randomized subjects should provide sufficient numbers for this study, assuming 66% of enrolled subjects will meet the requirements for inclusion in the micro-ITT population.

For the EMA, it is assumed that 65% of the randomized subjects will be in the micro-MITT population and 60% in ME population. The microbiological success rates at TOC are assumed to be 79% and 82% in both treatment groups in the micro-MITT and ME populations, respectively. With these assumptions, using an NI margin of 10%, a one-sided alpha of 0.005, and the sample size methodology of Farrington and Manning, there is at least 80% power to show NI for the co-primary efficacy outcomes. The power calculations are summarized in [Table 3](#) based on a total of 1200 randomized subjects.

Table 3 Assumptions of Sample Size Calculations

Outcome/Population	Alpha level (one-sided)	Evaluability Rate	Outcome Rates		Total N	Power
			ERV	ERT		
FDA Outcomes						
Responder at EOI/micro-ITT	0.025	66%	93%	94%	790	>99%
Responder at TOC/micro-ITT	0.025	66%	71%	72%	790	80.0%
EMA Outcomes						
Microbiological Success at	0.005	65%	79%	79%	780	79.8%

TOC / micro-MITT						
Microbiological Success at TOC / ME-TOC	0.005	60%	82%	82%	720	84.7%

Key: ERV = Eravacycline; ERT = Ertapenem; EMA = European Medicines Agency; FDA = Food and Drug Administration; ITT = Intent-to-Treat; ME = Microbiologically Evaluable; Micro-MITT = Modified Microbiological Intent-To-Treat; TOC = Test of Cure.

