For the calculation of sample size it is assumed that 66% of the randomized subjects will be in the micro-ITT population. It is also assumed that the responder rates (clinical cure and microbiological success) at EOI will be 93% and 94% in the eravacycline group and the ertapenem group, respectively and at TOC will be 71% and 72% in the eravacycline group and ertapenem group, respectively. For the EMA, it was assumed that 65% of the randomized subjects will be in the micro-MITT population and 60% in the ME population. The microbiological success rates at TOC are assumed to be 79% and 82% in both treatment groups in the micro-MITT and ME populations, respectively. With these assumptions, utilizing a 10% non-inferiority margin, and the sample size methodology of Farrington-Manning, 790 subjects (395 subjects per group) are required in the micro-ITT population and a total of 1200 subjects will be randomized. This sample size provides at least 80% power for the co-primary efficacy outcomes at EOI and TOC in the micro-ITT population as well as for the co-primary outcomes for the EMA.

Safety

Safety analyses will be conducted on the safety population. Subjects will be analyzed according to the treatments received.

Adverse Events

Verbatim descriptions of adverse events (AEs) will be mapped to Preferred Terms and System Organ Classes using Medical Dictionary of Regulatory Activities (MedDRA) and tabulated by treatment arm. The number and percentage of subjects who experience treatment-emergent AEs and serious AEs will be presented by reporting levels for System Organ Class and Preferred Term. Each subject will be counted once for each level of reporting. Tabulations by severity and by relationship to study drug, as reported by the Investigators, will also be provided. Deaths and premature discontinuations from study drug due to an AE will be identified.

Laboratory Data

Hematology, chemistry, coagulation, and urinalysis (where applicable) data will be summarized using shift tables based on toxicity criteria, change from baseline, and the number and percentage of subjects with clinically notable values. Clinically notable values will be specified in the Statistical Analysis Plan.

Other Safety Data

Physical examination data will be reported (as warranted) and analyzed as adverse events. Vital signs will be summarized using descriptive statistics for change from baseline and percentage of subjects with an abnormal value as defined in the SAP.

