Efficacy Assessments

Responder rates will be determined for each treatment arm overall and for the randomization stratification factors: (1) primary site of infection (pyelonephritis and normal urinary tract anatomy vs. all other diagnoses) and (2) receipt of a single dose of effective non-study antibiotics for the acute cUTI within 72 hours prior to randomization. The responder rate will be determined as the number of subjects with clinical cure (i.e., complete or significant improvement of signs or symptoms such that no further systemic antibiotic treatment is required) and microbiological success at the respective visit divided by the number of subjects in the analysis population (i.e., overall or by randomization strata). A two-sided 95% CI around the difference in the eravacycline and ertapenem responder rates will be determined using the Miettinen and Nurminen method. If the lower bound of the 95% CI for the difference in responder rates at EOI and TOC in the micro-ITT population is above -10% for both time points, noninferiority of eravacycline to ertapenem will be concluded.

For the EMA, the microbiological success rate will be determined as the number of subjects with microbiological success at the respective visit divided by the number of subjects in the analysis population. Microbiological success rates at TOC will be determined, along with two-sided 99% CIs, by treatment arm for subjects in the micro-MITT and ME populations. If the lower bound of the 99% CI for the difference in microbiological success rates at TOC is above -10% for both the micro-MITT and ME populations, noninferiority of eravacycline to ertapenem will be concluded.

Clinical outcome and microbiological outcome will be summarized by treatment group, time point and analysis population. Two-sided 95% CIs for the difference between treatment groups in clinical cure and microbiological success will be provided.

Microbiology

Purified bacterial pathogens aerobically cultured from urine using a calibrated loop to identify a quantitative count of bacteria at a lower limit of 10^3 CFU/mL and aerobic and anaerobic blood culture pathogens will be evaluated for susceptibility and the emergence of resistance to study drugs and overgrowth of non-susceptible organisms at a central laboratory.

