15.3 Sample Size Considerations

This study is designed to demonstrate non-inferiority of eravacycline to ertapenem in the co-primary efficacy measures of responder outcome at the EOI and TOC visits in the micro-ITT population. An NI margin of 10% will be used which is based on historical data regarding the treatment effect of antibiotics. A 10% NI margin for the efficacy measure of responder outcome is robust and can sufficiently confirm a clinically meaningful treatment effect of eravacycline in the treatment of cUTI.

The sample size calculation is based on ensuring sufficient power for the co-primary efficacy outcomes for the FDA as well as the co-primary efficacy outcomes for the EMA (which are secondary efficacy outcomes for the FDA). Using a 10% non-inferiority margin, one-sided alpha of 0.025, 80% power, response rates at TOC of 71% in the eravacycline group and 72% in the ertapenem group, and the sample size methodology of Farrington and Manning, a total of 395 subjects per arm in the micro-ITT population is required. This sample size provides >90% power for the response rates at EOI assuming the response rates are 93% and 94% in the eravacycline and ertapenem groups, respectively. A sample size of approximately 1200 randomized subjects should

provide sufficient numbers for this study, assuming 66% of enrolled subjects will meet the requirements for inclusion in the micro-ITT population.

For the EMA, it is assumed that 65% of the randomized subjects will be in the micro-MITT population and 60% in ME population. The microbiological success rates at TOC are assumed to be 79% and 82% in both treatment groups in the micro-MITT and ME populations, respectively. With these assumptions, using a non-inferiority margin of 10%, a one-sided alpha of 0.005, and the sample size methodology of Farrington and Manning, there is at least 80% power to show non-inferiority for the co-primary efficacy outcomes. The power calculations are summarized in Table 4 below based on a total of 1200 randomized subjects:

Table 4: Assumptions for Sample Size Calculations

Outcome/Population	Alpha level (one-sided)	Evaluability Rate	Outcome Rates		Total N	Power
			ERV	ERT		
FDA Outcomes						
Responder at EOI/micro-ITT	0.025	66%	93%	94%	790	>99%
Responder at TOC/micro-ITT	0.025	66%	71%	72%	790	80.0%
EMA Outcomes						
Clinical Cure at TOC/micro-MITT	0.005	65%	79%	79%	780	79.8%
Clinical Cure at TOC/ME	0.005	60%	82%	82%	720	84.7%

ERV=Eravacycline; ERT=Ertapenem

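### The EMA power of at least 80% is a per-endpoint figure; the chance of meeting both EMA co-primary endpoints is about 76–77%

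*SAP*

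**What the plan says.** **Power claim.** SAP 4.1 states that, under the EMA assumptions, there is "at least 80% power to show NI for the co-primary efficacy outcomes". Protocol 15.3 states that "there is at least 80% power to show non-inferiority for the co-primary efficacy outcomes". The protocol synopsis (Sample Size Estimation) claims at least 80% for the FDA pair "as well as for the co-primary outcomes for the EMA".

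**Support for it.** SAP Table 3 and Protocol Table 4 give one power per row. The EMA rows are micro-MITT at TOC (N = 780, 79.8%) and ME at TOC (N = 720, 84.7%), both at one-sided 0.005. No row or sentence gives the power to succeed on both.

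**Decision rule.** Under Efficacy Assessments in the synopsis, EMA success depends on whether the lower bound of the 99% interval "is above -10% for both the micro-MITT and ME populations, noninferiority of eravacycline to ertapenem will be concluded". Protocol 15.2.1 also requires both intervals to clear -10%.

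**The concern.** When a claim requires two endpoints to succeed, its power is the probability that both do. That is lower than either single-endpoint power unless the endpoints are perfectly dependent. Here the weaker row is already slightly under 80%, so the joint figure must be under 80% too. Someone using this section to judge the chance of a successful EMA claim would take 80% as a floor, when it lies above the attainable value.

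The FDA paragraph does not have this problem. EOI power is so high that the joint FDA power is in effect the TOC power, so the same style of statement is accurate for the FDA pair and not for the EMA pair.

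**Working it through.** **Inputs** (SAP 4.1 unless noted)

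- Margin and alpha: "using an NI margin of 10%, a one-sided alpha of 0.005".
- Success rates: "assumed to be 79% and 82% in both treatment groups in the micro-MITT and ME populations, respectively", so the true difference is zero.
- Population sizes: "it is assumed that 65% of the randomized subjects will be in the micro-MITT population and 60% in ME population". With 1200 randomized 1:1, this is 780 (390 per arm) and 720 (360 per arm).
- Nesting: SAP 3.1.7 draws ME from micro-ITT and CE, and SAP 3.1.6 requires at least 3 days of study drug for CE. Every ME subject is therefore in micro-MITT.
- Correlation of the two test statistics: not given in the documents. It is derived in step 2, and a range is shown in step 3.

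**Step 1. Single-endpoint power (Farrington-Manning)**

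Power = Φ[(0.10 − 2.576·s0)/s1]. Here s0 is the standard error from the rates fitted under a difference of -10%, and s1 is the standard error under the planned rates.

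- Micro-MITT: s1 = √(2·0.79·0.21/390) = 0.02917. Fitted null rates are 0.7316 and 0.8316, so s0 = 0.02937. Power = Φ(0.835) = **79.8%**, which reproduces the table.
- ME: s1 = √(2·0.82·0.18/360) = 0.02864. Fitted null rates are 0.7598 and 0.8598, so s0 = 0.02902. Power = Φ(0.882) = **81.1%**. The printed 84.7% does not reproduce at 360 per arm; it is what 390 per arm gives (84.7%). That is a separate matter, so both values are carried forward.
- FDA rows (395 per arm, one-sided 0.025): EOI 99.8% and TOC 80.1%, in agreement with the table.

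**Step 2. Correlation implied by the nesting**

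The micro-MITT difference contains the ME difference with weight 720/780 = 0.923. Hence ρ = 0.923 × 0.02864/0.02917 = **0.906**.

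The rates also imply success in the 60 non-ME subjects of (780·0.79 − 720·0.82)/60 = 25.8/60 = 43%.

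**Step 3. Joint power (bivariate normal)**

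| Correlation | ME row at 81.1% | ME row as printed, 84.7% |
|---|---|---|
| 0 | 64.7% | 67.6% |
| 0.80 | 73.5% | 75.4% |
| **0.906** | **75.7%** | **77.4%** |
| 0.95 | 76.9% | 78.4% |
| 0.99 | 78.8% | 79.6% |
| Ceiling (smaller row) | 79.8% | 79.8% |

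**Step 4. Simulation check**

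Nested populations were simulated with 400,000 trials per setting, using the Miettinen-Nurminen test at one-sided 0.005. Joint power was 76.0–76.1% when ME membership varied at random and 77.2–77.3% when it was fixed at 360 + 30 per arm. The simulated micro-MITT power alone was 80.0% and 80.9% respectively, so the 79.8% ceiling belongs to the Farrington-Manning approximation. The gap between single and joint power is present either way.

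**Step 5. FDA pair**

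Even if EOI and TOC were independent, joint power would be 0.9982 × 0.8008 = 79.9%.

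**The case against.** - **The table shows one row per endpoint, so a per-endpoint reading is available.** It is, and on that reading the sentence is right to rounding for micro-MITT. But the text never says the figure is per endpoint, and it attaches it to the co-primary outcomes as a set, for which the protocol defines a single decision.
- **Protocol 15.2.1 computes 99% intervals and then applies the rule to 95% intervals.** At one-sided 0.025 the same inputs give 92.7% and 93.4%, with about 91% jointly, so the claim would be met. That wording conflicts with the 99% intervals in the same paragraph, with the synopsis, and with the 0.005 on which the power statement itself rests. It needs correcting, but it does not support the claim as made.
- **The correlation is not in the documents.** True, and the exact figure depends on it. The nesting and planned rates nevertheless fix a natural value, and the table shows that no correlation brings the joint figure to 80%. The stratified analysis named for the EMA in Protocol 15.2.1 was not modelled.
- **The shortfall is small, and SAP 1.1.1 defers the EMA analysis to a separate SAP.** Both points are fair and limit the weight of the finding. The power claim is still made in this SAP and in the protocol, so it should be put right there.

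**Conclusion.** The concern holds. Power for the EMA decision is about 76–77%: 75.7% with the ME row recomputed at 720 subjects, 77.4% with the row as printed. The shortfall against the stated floor is roughly 3–4 points. This rests on the plan's own rates, sizes, margin and one-sided 0.005, on ME being nested in micro-MITT, and on equal success rates in the two arms, including among non-ME subjects. That the joint figure is below 80% needs no assumption about correlation once the table's 79.8% is accepted.

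The effect is confined to the forecast for the EMA objective. Type I error, the decision rule and the FDA primary claim are unaffected.

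**What to change.** In SAP 4.1 and Table 3, Protocol 15.3 and Table 4, and the synopsis:

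1. Label the two EMA rows as power for each endpoint taken alone.
2. Replace the EMA sentence with one along these lines: *Power to show non-inferiority in both the micro-MITT and ME populations is about 76%, at one-sided 0.005, under the rates and sizes in the table and with ME nested in micro-MITT (implied correlation about 0.91).* The 76% goes with an ME row of 81.1%. If the printed 84.7% can be justified, the figure is about 77%.
3. In Protocol 15.2.1, reconcile the 95% and 99% intervals, because the power statement is valid only for the latter.

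The cost is wording, plus one stated figure that becomes less favourable. No change of sample size is required. For reference, 80% joint power under the same assumptions would need about 1304 randomized subjects, against 1200 planned.
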